9.7 STUDY STOPPING RULES

The overall study will be paused, and appropriate authorities (e.g., IRB, Knight Data and Safety Monitoring Committee) notified if the following events occur:

- Life-threatening grade 4 toxicity attributable to protocol therapy that is unmanageable, or unexpected.
- Death suspected to be related to Optune® device.

10. STATISTICAL CONSIDERATIONS

Refer to Section 3.1, *Description of the Study Design* for a detailed description of the study design and endpoints.

10.1 ANALYSIS POPULATIONS

This is a phase II multi-center single-arm pilot study to evaluate the incidence of metastatic brain lesions in participants with SCLC that receive TTField therapy. All participants that initiated TTField therapy will be considered evaluable for efficacy analysis. All participants who initiated TTFields therapy (regardless of duration) will be considered evaluable for safety. The anticipated enrollment is 106 participants, of which 45 participants will have ESCLC and 61 participants will have LSCLC.

10.2 DESCRIPTION OF STATISTICAL METHODS

ANALYSIS OF PRIMARY ENDPOINT

The primary endpoint is the incidence of SCLC brain metastases following 6 months of TTField therapy. Descriptive statistical analysis will be conducted for all participants, overall and by disease group (extensive stage and limited stage). The incidence rate of SCLC brain metastases at 6 month will be reported with 95% confidence interval, overall and by disease group (extensive stage vs. limited stage), by type (infratentorial vs. supratentorial). One sample test of proportion will be used to determine if the incidence rate is significantly reduced compared to historical controls for each disease group (assumed to be 40% and 30% for extensive stage and limited stage, respectively). Logistic regression model will be conducted to identify if there is any center difference (Oregon, Washington, Arizona, vs Ohio) after controlling for other covariates (for example, the compliance of patients in using the device) of that may influence the incidence of SCLC brain metastases. Expecting the models for extensive stage and limited stage could be quite different, we will start with fitting two separate logistic regression models for each disease group. In addition to the above listed variables, patient characteristics, tumor characteristics will also be included as covariates to start the model building. Specifically, for each disease group, we will fit univariable logistic regression model for all potential covariates. Variables with p-value < 0.25 in the univariable logistic regression model will be included to build multivariable logistic regression model. Purposeful selection method combined with Akaike Information Criteria (AIC) will be used for final model determination for each disease group. If it turned out that the two final models have similar covariates and effect size, we will also develop a pooled logistic regression model using all subjects. The pooled logistic regression model will force the disease group as a covariate to the model, and all other variables included in the model will be carefully evaluated for confounding effect and for potential interaction with disease group.

ANALYSIS OF THE SECONDARY ENDPOINTS

For incidence of SCLC brain metastases following 12 months of TTField therapy, we will use exactly the same approach as described in Section 10.2.1.

The distribution of overall survival will be graphically described using Kaplan-Meier plot, for all subjects together, and for each disease group (extensive stage and limited stage). If estimable, the median survival time will be reported with 95% confidence interval. The analysis is just for description. No hypothesis testing is planned for this endpoint. However, we will fit two cox

proportional hazard regression model to identify risk factors that may impact the OS. Covariates evaluated in the univariable analysis in Section 10.2.1 will also be evaluated in the cox proportional hazard regression model. OS at 6, 12, 24, 36 and 60 months after completion of TTField therapy will be reported.

We will estimate TTField therapy-related toxicity and along with an exact confidence interval using the safety set. A summary table of observed AEs will also be reported by disease group (extensive stage and limited stage).

The Quality of life scores will be recorded over time (See Section 7.8 for details) using the EORTC QLQ-C30 questionnaire. Summary of QoLs and its change over time will be presented graphically using box plot and spaghetti plot, in addition to a summary table of QoL over time. No hypothesis testing is planned for QoL.

Incidence of cognitive AEs will be assessed by measuring changes in MMSE scores over time. Descriptive statistical analysis will be conducted on the endpoint. (See Section 7.8 for details on time points for measurement)

To evaluate how the time of last cycle of chemotherapy or chemoradiation therapy impact our observed incidence of SCLC brain metastases, we will also conduct a parallel analysis using SCLC brain metastases rate at 6-month from the beginning of the 4th cycle of chemotherapy to development of brain metastases as a secondary endpoint. We will use exactly the same approach as described in Section 10.2.1.

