10.3 SAMPLE SIZE, POWER, ACCRUAL RATE AND STUDY DURATION

SAMPLE SIZE AND POWER

A total of 106 participants with SCLC will be accrued into this study of which 45 and 61 participants will be characterized as having either ESCLC or LSCLC disease, respectively. For ESCLC, we need 45 subjects for 80% power to detect a 50% reduction at a 5% significance level using a two-sided exact test for one proportion, assuming the incidence rate is 40% for subjects not receiving Optune®. PASS 15 “Test for one proportion” procedure was used for sample size computation. We will use two-sided exact test for one proportion to test the incidence rate against the null hypothesis of 40%. $P < 0.05$ will be considered statistically significant.

For participants with LSCLC, we need 61 subjects for 80% power to detect a 50% reduction at a 5% significance level, using a two-sided exact test for one proportion, assuming the incidence rate is 30% for subjects not receiving Optune®. PASS 15 “Test for one proportion” procedure was used for sample size computation. We will use two-sided exact test for one proportion to test the incidence rate against the null hypothesis of 30%. $P < 0.05$ will be considered statistically significant.

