10.4 HANDLING OF MISSING DATA

Every attempt will be made to obtain data at the defined time points as described in the primary and secondary endpoints. For time points that have no data, we will evaluate whether or not the other time points can be used to fulfill the primary and secondary data. If the data are not sufficient to analyze specific endpoints, the participant's data may be excluded entirely or

partially, depending on the specific endpoints in question and in consultation with the biostatistician. No missing data will be imputed. Whenever possible, all available data will be included in the analysis. A sample size for each analysis will be clearly stated along with the reason for exclusion, if any participant is excluded from the analysis due to missing data.

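### By cross-reference, Section 10.2.2 tests 12-month brain-metastasis incidence against the 40%/30% that serve as the 6-month null, so the 12-month null is too low

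*Combined protocol and SAP*

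**What the plan says.** Section 10.2.1 (analysis of the primary endpoint) plans three things for 6-month incidence: an estimate with a 95% CI, a one-sample test against historical controls in each stage, and logistic models. The historical rates are "assumed to be 40% and 30% for extensive stage and limited stage, respectively". Section 10.3.1 names the test. For extensive stage: "We will use two-sided exact test for one proportion to test the incidence rate against the null hypothesis of 40" percent. The limited-stage sentence is the same with 30%.

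Section 10.2.2 then carries this over twice:
- 12-month incidence: "For incidence of SCLC brain metastases following 12 months of TTField therapy, we will use exactly the same approach as described in Section 10.2.1".
- A parallel analysis of the "SCLC brain metastases rate at 6-month from the beginning of the 4th cycle of chemotherapy": "We will use exactly the same approach as described in Section 10.2.1".

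No separate null is given for either. The same section expressly rules out testing for overall survival ("No hypothesis testing is planned for this endpoint") and for quality of life ("No hypothesis testing is planned for QoL"), and calls the MMSE analysis descriptive. It makes no such exception for the two brain-metastasis secondaries.

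Section 3.2 defines the 12-month endpoint as the incidence of any brain metastasis from the start of TTFields. It starts the other clock at chemotherapy cycle 4.

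**The concern.** A one-sample test is only as good as the match between its null and its endpoint. The three endpoints differ in window (6 or 12 months) or in origin (device start or cycle 4), yet the cross-reference gives them one pair of null values.

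At 12 months the mismatch has a known direction. Everyone with a metastasis by month 6 also has one by month 12, so the untreated 12-month rate can equal the 6-month rate only if no untreated patient has a first brain metastasis in the second half-year. The protocol's own background (Section 1.1) points the other way: it puts the actuarial risk at nearly 80% within 2 years of diagnosis. A p-value against 40%/30% at 12 months therefore mixes the device effect with six extra months of accumulating events. A device that met its 6-month target could fail the 12-month test, and an inert device could be reported as significantly worse than history.

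**Working it through.** **1. The plan's own design.** Inputs from Section 10.3.1: n = 45, 40% against 20% (ES); n = 61, 30% against 15% (LS); two-sided exact test at 5%, taken as 2.5% per tail.
- ES: significantly lower if 11 or fewer of 45 (P = 2.16% under 40%), significantly higher if 26 or more. Power at 20% is 82.6%.
- LS: significantly lower if 11 or fewer of 61 (P = 2.48% under 30%), significantly higher if 26 or more. Power at 15% is 80.4%.

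45 and 61 are the smallest sample sizes with at least 80% power, so the primary arithmetic reproduces. The same cut-offs apply at 12 months if the null is reused.

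**2. Assumptions for the 12-month illustration (not given in the documents).**
- 40%/30% are untreated 6-month rates, and the device meets 20%/15% at 6 months.
- Deaths without metastasis stay in the denominator as non-events.
- Median time to such death, from device start, is 5-8 months (ES) and 12-15 months (LS). These lie below the background's 9 to 10 and about 18 months of survival, the first of which is counted from diagnosis.
- The metastasis hazard is constant, or is multiplied by r = 0.5 or r = 0.25 after month 6.

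**3. Formula.** With monthly death hazard d = ln 2 / median and metastasis hazard m, incidence by t months is m/(m+d) × [1 − exp(−t(m+d))]. Solve for m from the 6-month rate. The 12-month rate adds exp(−6(m+d)) times the same expression for a further 6 months with hazard r·m.

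Example, ES, median 5, r = 1: d = 0.1386. For 40% at 6 months, m = 0.1361, and the 12-month rate is 0.1361/0.2747 × [1 − exp(−12 × 0.2747)] = 47.7%. For 20% at 6 months, m = 0.0566, and the 12-month rate is 26.2%. Then P(11 or fewer of 45 at 26.2%) = 47%. A null of 47.7% would reject at 14 or fewer, with power 82%.

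**4. Results at 12 months** (shortest median first):

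| | 12-month rate, inert | 12-month rate, target | Power vs 40%/30% | Power, matched null | Inert called worse | Inert false win |
|---|---|---|---|---|---|---|
| ES, r = 1 | 47.7-51.9% | 26.2-28.9% | 47-32% | 82-87% | 11-26% | 0.1% or less |
| ES, r = 0.5 | 44.5-46.9% | 23.3-24.7% | 65-56% | 85-88% | 5-9% | 0.4-0.2% |
| ES, r = 0.25 | 42.5-43.7% | 21.7-22.5% | 74-70% | 84-81% | 3-4% | 0.9-0.6% |
| LS, r = 1 | 43.8-45.0% | 23.7-24.4% | 19-16% | 89-91% | 62-69% | under 0.1% |
| LS, r = 0.5 | 37.6-38.2% | 19.6-19.9% | 46-43% | 87-86% | 25-28% | 0.1% or less |
| LS, r = 0.25 | 34.0-34.3% | 17.3-17.5% | 64-62% | 84-83% | 10-11% | 0.5-0.4% |

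**5. Cycle-4 clock.** Section 4.1 requires a metastasis-free brain MRI within 12 weeks of enrollment, and this clock starts before that MRI. A patient with a metastasis found in between cannot enrol, so some of the 6 months may be event-free by selection. With w such weeks, the inert rate is the step-3 incidence over (26 − w)/26 of 6 months. At w = 0 it is 40%/30% and there is no bias. At w = 3 an inert device wins in about 4-5% (ES) and 6% (LS) of trials; at w = 6, in about 8-10% and 13-14%. The documents do not give w.

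**The case against.** **The numbers are not printed for the secondaries.** The shared approach also covers estimates, CIs and logistic models, so one could say that the secondary null is simply unspecified. That is possible. But the plan says exactly the same approach, offers no other null, and rules out testing by name elsewhere. Reuse is the natural reading, and either reading calls for the same edit.

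**The error is conservative for efficacy.** This stands. Section 10.2.1 asks whether incidence is reduced, and an inert device falsely wins at 12 months at most about 0.9% (ES) and 0.5% (LS) of the time, below the nominal 2.2%/2.5%. The harm is lost power and a misleading adverse signal.

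**The sizes rest on assumptions.** This also stands. The direction follows from the definition of the endpoint; the amounts do not.

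**Cycle 4 is a parallel analysis** of how chemotherapy timing affects the observed rate, not a separate efficacy claim, and its bias can be nil. That is why it is only a note here.

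**A reader might infer that the primary test is unsafe,** because 40%/30% carry no stated window, origin or source and could be 12-month rates. The documents do not support this. The Synopsis places the sample-size assumption directly under the 6-month endpoint, and Section 10.2.1 defines the 6-month rate before testing it. The background figure is compatible too: at constant hazard, 80% at 24 months gives 1 − 0.2^(1/4) = 33% at 6 months (illustrative only, since its origin is diagnosis and stages are mixed).

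**Conclusion.** The 12-month test, as cross-referenced, uses a null that is too low. On the assumptions listed, a device that meets its 6-month target has 12-month power of about 32-74% (ES) and 16-64% (LS), against about 81-91% with a matched null. An inert device is called significantly worse in about 3-26% (ES) and 10-69% (LS) of trials. The cycle-4 null may be too high, by an unknown amount that can be zero.

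The severity is minor. No decision rule or sample size rests on either secondary, and false efficacy claims at 12 months are not inflated.

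A reader might also infer near-zero 12-month power if metastasis-free deaths were dropped under Section 10.4 ("If the data are not sufficient to analyze specific endpoints", a participant's data may be excluded). That would combine the loss of patients with the wrong null. It is also not the plan's default, because Section 10.1 makes everyone who starts therapy evaluable for efficacy. What does remain is that neither section says how a death before 12 months is counted.

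**What to change.** In Section 10.2.2, for both secondaries, do one of the following:
- Exclude the one-sample test against 40%/30%, and report incidence by stage with the 95% CI already planned.
- State a sourced null per stage matched to the endpoint's window and origin. For the cycle-4 endpoint it must also match the condition of being metastasis-free at entry.

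State how deaths before 12 months are counted. In Section 10.2.1, state that 40%/30% are 6-month rates from a time comparable to the start of TTFields, and give their source.

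This is SAP wording. The cost is at most two secondary p-values; design, sample size and data collection are unchanged.

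### The 12-month and 4th-cycle brain-metastasis endpoints inherit the primary significance test with no testing order or exploratory label, so a stage that fails its 6-month test can still be called significantly reduced

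*Combined protocol and SAP*

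**What the plan says.** Section 10.2.1 (Analysis of Primary Endpoint) makes 6-month incidence from the start of TTFields the primary endpoint: "One sample test of proportion will be used to determine if the incidence rate is significantly reduced compared to historical controls for each disease group". The historical rates are 40% for extensive stage (ES) and 30% for limited stage (LS). Section 10.3.1 specifies a two-sided exact one-proportion test for each stage, significant at P<0.05. The sample sizes follow from it: for ES, "we need 45 subjects for 80% power to detect a 50% reduction at a 5% significance level using a two-sided exact test"; for LS, "we need 61 subjects for 80% power to detect a 50% reduction at a 5% significance level, using a two-sided exact test".

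Section 10.2.2 (Analysis of the Secondary Endpoints) returns to this method twice. On the 12-month endpoint: "For incidence of SCLC brain metastases following 12 months of TTField therapy, we will use exactly the same approach as described in Section 10.2.1". On 6-month incidence from the beginning of the 4th chemotherapy cycle, introduced as a parallel analysis: "We will use exactly the same approach as described in Section 10.2.1".

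The same section treats other secondaries differently. On overall survival: "No hypothesis testing is planned for this endpoint". It says the same of quality of life and calls the MMSE analysis descriptive. Section 10 contains no adjustment, formal testing order, alpha split or exploratory label for the two brain-metastasis secondaries.

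**The concern.** Two stages and three windows give six significance tests of essentially one question: does the device reduce brain metastases? The plan separates tested from untested secondaries, and its wording puts these two on the tested side. Nothing says what follows if a stage's 6-month test is not significant but its 12-month or 4th-cycle test is.

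At stake is the claim that a stage's incidence was significantly reduced. The trial is single-arm against fixed historical rates, so no concurrent control can expose a chance result. The 4th-cycle window needs particular care. Its clock starts before Day 1, while inclusion criterion 6 requires no brain metastases on the enrolment MRI, so part of the window is close to event-free by design.

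**Working it through.** **Inputs from the documents.** ES: n=45, null 40%, alternative 20%. LS: n=61, null 30%, alternative 15%. Two-sided exact test, P<0.05 (10.3.1). Windows: 6 and 12 months from Day 1, and 6 months from cycle 4 (3.2).

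**Assumed, because the documents do not say.** Constant hazard; a lag L of 1 to 3 months from cycle 4 to Day 1; the 40% and 30% refer to 6 months from Day 1; everyone is free of brain metastases on Day 1; no deaths or missing scans.

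**1. The plan's own figures reproduce** (equal-tailed exact test, 2.5% per tail).
- ES rejects at ≤11 or ≥26 of 45: lower tail 0.0216, upper 0.0120, size 0.0336, power 0.826.
- LS rejects at ≤11 or ≥26 of 61: lower tail 0.0248, upper 0.0246, size 0.0494, power 0.804.
- 45 and 61 are the smallest n that reach 80% power.

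**2. The two primary tests alone.**
- False reduction in at least one stage: 1 − (1 − 0.0216)(1 − 0.0248) = 0.046.
- Either direction: 1 − (1 − 0.0336)(1 − 0.0494) = 0.081.

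**3. All six tests, each window given its own correct null.** With constant hazard, p(t) = 1 − (1 − p0)^(t/6).
- 12 months: ES 1 − 0.6² = 0.64; LS 1 − 0.7² = 0.51.
- The 4th-cycle window covers t = 6 − L months after Day 1. For L = 1 the rates are 0.347 (ES) and 0.257 (LS); for L = 3 they are 0.225 and 0.163.

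The counts are nested in the same patients, and the stages are independent. Simulation gives:

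| Lag (months) | Any false reduction | False reduction on a secondary, that stage's primary not significant | Any rejection, either direction |
|---|---|---|---|
| 1 | 7.6% | 3.1% | 14.3% |
| 2 | 7.7% | 3.2% | 15.5% |
| 3 | 8.6% | 4.2% | 16.1% |

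Repeat runs agree within about 0.2 points (up to 8.7% at L = 3). Varying the hazard shape, with lags of 0.5 to 3 months, gives 7.1–9.3% for any false reduction; minimum-likelihood exact p-values take it up to 10.9%. The either-direction figure depends on correlation between windows. It runs from 8.1% (perfect correlation within stage, exact sizes) to 1 − 0.95⁶ = 26.5% (independent, nominal 5%).

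**4. The 40% and 30% nulls applied literally to every window.** The cut-off for a reduction is then ≤11 in every window.
- *12 months.* In the same patients, cumulative 12-month events cannot be fewer than 6-month events. At most 11 at 12 months implies at most 11 at 6 months, so this window cannot replace a failed primary: 0%.
- *4th cycle.* Events here cannot exceed 6-month events. The chance of a significant reduction here but not at 6 months is P(≤11 in 6 − L months) − P(≤11 in 6 months).

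| Lag | ES | LS | At least one stage |
|---|---|---|---|
| 1 | 0.0972 − 0.0216 = 0.0756 | 0.1073 − 0.0248 = 0.0825 | 1 − 0.9244 × 0.9175 = 0.152 |
| 2 | 0.3189 − 0.0216 = 0.2973 | 0.3386 − 0.0248 = 0.3138 | 1 − 0.7027 × 0.6862 = 0.518 |
| 3 | 0.6945 − 0.0216 = 0.6729 | 0.7121 − 0.0248 = 0.6873 | 1 − 0.3271 × 0.3127 = 0.898 |

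**5. After the fix.** Two primary tests remain: 4.6% for a false reduction, 8.1% in either direction. No secondary reduction can be claimed in a stage whose primary failed.

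**The case against.** The strongest reply is that this is a phase II pilot with one named primary endpoint, the other windows ranked as secondary, and a 95% CI reported with each incidence. The 4th-cycle analysis has a sensitivity purpose: to see how the timing of prior therapy affects the observed rate. Formal alpha control over such endpoints is not always expected. The P<0.05 threshold appears only in 10.3.1, for the 40% and 30% tests, so its use for the secondaries is an inference. All of that stands. It does not settle what may be claimed from a secondary test, because 10.2.2 sends these endpoints to a section whose core is a significance test and exempts other endpoints by name.

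A reader might infer three stronger things that the documents do not support.

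- *That the plan promises 5% and delivers 14–16%.* It states 5% per stage and no family-wise rate, and each primary test keeps its own level. The 14–16% also counts significant increases, rests on assumed hazards, lags and window-specific nulls, and includes about 8 points from the two primaries.
- *That there is no hierarchy at all.* Endpoints are ranked; only a formal testing order is missing.
- *That every secondary window offers an escape from a failed primary.* Under the literal nulls, the 12-month window does not when the same patients are analysed. Different exclusions by endpoint, which 10.4 allows, could change that.

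**Conclusion.** The gap is real and modest in general, but potentially large for the 4th-cycle window. With a correct null for each window, ungated secondaries raise the chance of some false reduction from 4.6% to about 7.6–8.7%. In about 3–4% of trials the false reduction falls in a stage whose own primary is not significant. With the literal 40% and 30%, the 4th-cycle window produces that outcome in roughly 15–90% of trials, because it compares a shorter time at risk with a 6-month rate. These sizes depend on the constant hazard, the 1-to-3-month lag and the origin assumed for the historical rates, none of which is in the documents. The qualitative point needs none of them: the text permits a significance claim on a secondary window after a failed primary. The absence of historical rates specific to the secondary windows is a separate gap.

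**What to change.** In 10.2.2:
- Report the 4th-cycle window by estimate and 95% CI only, with no test.
- Test 12-month incidence in a stage only if that stage's 6-month test shows a significant reduction, or report it by estimate and 95% CI only, in line with the no-test treatment of survival and quality of life. If it is tested, state the historical 12-month rate used as the null.

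In 10.2.1, state that each stage's primary test supports a claim for that stage only.

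The cost is a few sentences, with no added patients, visits or data. The primary cut-offs (≤11/45 and ≤11/61) and the stated 80% power do not change. The downside is that a secondary window can no longer be called significant when its stage's primary fails.

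This does not bring the study-wide rate across the two primaries to 5%; it stays at 8.1% in either direction. Splitting alpha at 2.5% per stage would do so, but at the present sample sizes power would fall to 72.0% (ES) and 69.7% (LS). The split is unnecessary if claims stay stage-specific.
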